Real World Observational Database for COVID-19 Treatment and Outcomes

Principal Investigator: [name] MD

Document type: Non-interventional study protocol

Version number: 05, Contains Amendment 4

Release date: Amendment IV
October 2-2020

Confidential and Proprietary

Not for Publication

The information in this document contains information that are privileged or confidential and may not be disclosed unless such disclosure is required by federal or state law or regulations. In any event, persons to whom the information is disclosed must be informed that the information is privileged or confidential and may not be further disclosed by them. These restrictions on disclosure will apply equally to all future information supplied to you which is indicated as privileged or confidential.

Table of contents

1	Responsible Parties.....	3
2	Brief Synopsis	4
	Amendments and Updates	6
3	Rationale.....	7
4	Registry Objectives	8
5	Research Methods	8
	5.1 Registry Design and Collection.....	8
	5.2 Analytic Design	9
	5.3 Registry Population	10
	5.4 Site Responsibilities.....	10
	5.5 Registry Data Collection.....	10
	5.6 Variables	11
	5.7 Data Analysis	12
	5.8 Quality Control	12
6	Protection of Human Subjects	12
7	Disseminating and Communicating Registry Results	15
8	Data Ownership	16
9	References	16

1 Responsible Parties

Table 1-1 Main responsible parties

Principal Investigator	[name] MD John Theurer Cancer Center at Hackensack University Medical Center [name]
Principal Analytic Group	COTA [name] [contact]
Participating Centers	Hackensack Meridian Health Network

2 Brief Synopsis

The principle objective of this observational database is to build research-grade real world data that will serve as platform to advance the scientific understanding and clinical care of patients with COVID-19.

1. Demographic, diagnostic, treatment and outcome data from centers throughout the Hackensack Meridian Health Network will be abstracted from the electronic health records of patients with confirmed or suspected COVID-19. This will be purely observational and no direction as to the care of the patient will be performed as part of this effort. There will be no research intervention(s) with the exception of collection of data from subjects currently receiving treatment or will/ or have had treatment at Hackensack Meridian Health Network. Data will be collected both retrospectively and prospectively.

1a. Data points to be collected will include, but are not limited to: age, gender, zip code, prior evaluation for COVID-19, tobacco history, race, site of care, healthcare worker, nursing home care, visits to ER, presenting features of fever/ cough/ dyspnea/ gastrointestinal/ mental status changes, days of symptoms, comorbidities, uses of antihypertensives, duration of hospitalization/ ICU care, presenting laboratory functions, presenting vital signs, need for oxygen support, dialysis/ ecmo use, treatment with hydroxychloroquine/ azithromycin/ remdesivir/ tocilizumab/ anti-inflammatory agents, arrhythmias/ QTc prolongation, enrollment on clinical trial, positive cultures, survival and cause of death. Additional data points may be added as needed however these points will only be collected related to their treatment and treatment related outcomes.

2. The data will be entered into a central HMH database hosted within the REDCap system (HIPAA compliant, secure)]

3. A de-identified dataset will be sent to COTA for primary statistical analysis as requested by the research teams. COTA will also make available a data/analytic visualization tool (hosted on Tableau) for analysis by primary investigators.
4. De-identified data may also be sent directly to HMH investigators for their own analysis after appropriate Human Subject Protection Review.
5. Data may be made available to governmental agencies as requested.

Amendments and Updates

Amendment number: 04

Date: October 2, 2020

Table 2-1 Study protocol amendments and updates

Number	Date	Section of study protocol	Amendment or update	Reason
01	April 5, 2020	Title Changed to capture RWD Outcomes for CoVID Population in HMHN.		Protocol will now allow for RWD Outcomes. This information will be utilized to determine best treatment options for CoVid Population.
02	April 23, 2020	Section 7.3		The HMH Biorepository (BioR) will be granted access to the database.
03	June 17, 2020	Section 7.4		The University of Miami will be granted access to only de-identified portions of the database.
04	August 20, 2020	Section 7.3		HMH Biorepository (BioR) collection clarification.
05	October 2, 2020	Section 5.1 and 7.3		Adding BI as a source of data in addition to EPIC.

3 Rationale

3.1 Rationale for an Observational Database in COVID-19

Coronavirus disease 2019 (COVID-19) is a respiratory tract infection caused by SARS-CoV-2 virus, a novel betacoronavirus discovered in Wuhan, China in December 2019. Subsequently, the disease has spread globally and outbreaks have been identified in over 100 countries. In China, data extracted from medical records of 1099 hospitalized patients and outpatients with laboratory confirmed COVID-19, revealed a summary of clinical characteristics. The most common symptoms were fever (43% on admission and 88.7% during hospitalization), cough (67.8%) and diarrhea (3.8%). On admission, ground-glass opacity was the most common radiologist finding on CT scans (56.4%). According to another recent Chinese study evaluation of 72,314 cases, 80% of patients presented with mild disease and the overall case-fatality rate was about 2.3%. (1)

A more complete understanding of the epidemiology, presenting features, role of comorbidities in severity of illness, needs for and utilization of healthcare resources, effectiveness of therapeutic approaches including off-label use, and clinical outcomes is desperately needed. Well-designed clinical trials, although helpful in gaining regulatory approval of new agents, enroll only a fraction of available patients and may not always mirror “real world” scenarios. An outcome database may be able to provide rapid indicators of effective strategies. Collecting data from the electronic health records permits significantly detailed information to be analyzed while not interfering with the routine best medical care delivered by the treating physicians.

4 Registry Objectives

The principle objective of this Observation Outcomes Database is to build research-grade real world data that will serve as a platform to advance the scientific understanding and clinical care of patients with COVID-19 in order to provide best clinical treatment options.

4.1 Primary Objectives

- 4.11 Understand epidemiology including presenting features of the COVID-19 pandemic within the Hackensack Meridian Network
- 4.12 Explore the impact of co-morbidities and other patient factors on the severity of COVID-19
- 4.13 Understand need for hospitalization, ICU support and other healthcare resources among patients with COVID-19
- 4.14 Explore efficacy and toxicity of various treatment strategies including “off-label use” of medications in real world settings
- 4.15 Measure clinical outcomes including hospital discharges and survival

5 Research Methods

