5.1 Registry Design and Collection

The Hackensack Meridian Health RWD Observational COVID-19, a descriptive observational database, is a multi-center initiative collecting data throughout the Hackensack Meridian Health Network (HMH).

The database will be drawn from the electronic health records of patients with confirmed or suspected COVID-19. HMH utilizes the EPIC system at most of the facilities, which will serve as the primary data source. Additional data obtained via other HMH staff and

bioinformatics can be added to the database as available and permitted. This includes but is not limited to data obtained either directly from EPIC or provided by other sources such as the HMH Business Intelligence Office (BI) to facilitate data extraction. Reports provided by BI can be entered directly into the REDCap database or kept separately (as pre-data supplements that might be added at a later time).

The database will be designed within the REDCap system. REDCap is a secure web application for building and managing online surveys and databases. While REDCap can be used to collect virtually any type of data (including 21 CFR Part 11, FISMA, and HIPAA-compliant environments), it is specifically geared to support online or offline data capture for research studies and operations.

The REDCap hosted universal observational database can export HIPAA compliant files for external analysis as part of the secondary research usage clause defined by the OHRP.

Data collection fields enumerating the common prognostic variables, treatment regimens and clinical outcomes have been designed by the principal investigator and the study team with input from the Centers of Disease Control and Prevention (CDC).

The abstraction process into the database will be performed by members of HMH who are approved to have access to the EPIC system or provided by BI. Outside abstraction, which would involve viewing of PHI, will not be permitted unless specifically granted by the IRB.

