5.6 Variables

Data points will be collected from the electronic medical record (or other HMH sources as available for patients with confirmed or suspected COVID-19. A partial listing is detailed below:

- 5.61 Key demographic variables include age, gender, race, zip code, past medical history documented co-morbidities, smoking history, etc.
- 5.62 Key diagnostic variables include date of diagnosis (COVID testing), blood count at time of hospitalization and/or entry to ICU care, chemistry panel, ferritin, ddimer, c-reactive protein, IL-6 levels, etc.
- 5.63 Key therapeutic variables include use of hydroxychloroquine, azithromycin, ventilator support, dialysis support, pressor support, etc.
- 5.64 Key outcome variables include will include need for hospitalization, duration of hospitalization, need for icu/ventilator support, duration of icu support, and death..

5.65 Key treatment center variables include hospital type (academic/ community), number of cases per hospital.

Data Analysis

5.71 COTA will provide basic descriptive analysis of the COVID-19 patients in a de-identified aggregated fashion. Survival and healthcare utilization analysis with time variables will utilize censoring and the Kaplan-Meier methodology. Multi-variable analysis for associations between demographic and/or treatment variables and key outcomes will be performed. Additional analysis will be performed per review of the data.

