6.1 Informed Consent

The Principal Investigator believes that the elements for a full waiver of consent under 45 C.F.R. §46.116 are met. Specifically, in order to waive consent the following requirements must be met:

- (1) The research involves no more than minimal risk to the subjects;
- (2) The waiver or alteration will not adversely affect the rights and welfare of the subjects;
- (3) The research could not practicably be carried out without the waiver or alteration; as COVID-19 populations have received treatment and have been discharged or deceased.

The study protocol represents an observational review of patients with confirmed or suspected COVID-19. No interventions are required for enrollment of patients into this database. There will be no direct contact any patient. Protected health information (PHI) will not be made available (pursuant to the HIPAA Privacy Rule as described below) and only aggregate data will be disclosed. The data collection will be conducted across HMH network drawing information from a variety of healthcare settings, with data drawn principally from the electronic health records utilized by the network. It would not be practical (item 3) by the Investigators to obtain consent across the network (which includes multiple hospitals and clinics across the state) as no contact will occur between the study team and the potential subjects. This is an observational study. The subjects will be receiving standard of care therapy at multiple sites, with their consent for the care per usual practice, and will not be made aware of the collection of the data nor will their treating physicians as to keep the therapy unbiased by participation in this study.

Furthermore, this study will involve only collection of data that has or will be obtained for care of the patient/subject. Thus the study may be considered “secondary research” under the revised common rule that became effective January 2020. Unlike the pre-2018 rule exemption for secondary use of information and biospecimens, the Final Rule has no requirement that the information and biospecimens must be pre-existing at the time that the investigator begins the research; prospective collection is permitted.

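### Survival is a primary objective, but deaths outside the network are incompletely captured and no horizon or censoring rule is set, so the estimate is biased in a direction the plan leaves open

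*Combined protocol and SAP*

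**What the plan says.** - **Objective and fields.** Item 4.15 under 4.1 Primary Objectives is to "Measure clinical outcomes including hospital discharges and survival", with no time point. Brief Synopsis item 1a collects "positive cultures, survival and cause of death", and item 5.64 lists "need for icu/ventilator support, duration of icu support, and death" among the key outcomes. None of these says whether death means in hospital, by a fixed day, or at any time.
- **Sources.** Section 5.1 states: "The database will be drawn from the electronic health records of patients with confirmed or suspected COVID-19". It adds: "HMH utilizes the EPIC system at most of the facilities, which will serve as the primary data source". Further data may come from network staff and bioinformatics, or be "provided by other sources such as the HMH Business Intelligence Office (BI) to facilitate data extraction". The list is open-ended and 5.6 allows other network sources, but no death index, vital-records, claims or hospice linkage is named.
- **Contact.** Section 6.1 says "There will be no direct contact any patient".
- **Analysis.** Item 5.71 specifies censoring and Kaplan-Meier for survival, and multi-variable analysis of key outcomes. It gives no time origin, no censoring date and no handling of discharge.
- **Follow-up.** The synopsis says collection is both retrospective and prospective. No duration, minimum follow-up or data cut is given.
- **Population and fields.** Section 5.3 does not require hospitalisation. Nursing home care is a listed data point. Discharge destination and hospice are not listed, but the protocol calls its lists partial.

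**The concern.** Once a patient leaves a network facility, a death at home, in a care facility or in another health system enters the database only if someone in the network happens to chart it. The study team cannot ask, and no outside record is named to fill the gap. Follow-up also differs between patients, because old and new cases enter together with no common horizon.

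A survival estimate then depends on how patients discharged alive are treated, and the plan does not say. They could be carried as alive to the data cut, or censored at discharge. The first counts unseen deaths as survival. The second assumes that discharged patients would have gone on dying at the rate of those still in hospital, which is seldom plausible.

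At stake are the survival figure of 4.15 and the contrasts of 4.12, where comorbidities and other patient factors are related to severity. If unseen deaths are more common in some groups than in others, those contrasts move too. Section 4 describes the data as research-grade and meant to inform treatment options, so the figures will be used.

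**Working it through.** The protocol states no survival rate, event count or sample size, so it has no figure to reproduce. The check asks how large the bias could be and which way it runs. **Every rate below is an assumption; none comes from the documents.**

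**1. Overall survival at day T = 28**

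Inputs: constant hazards in hospital; mean stay 10 days, so the total exit rate is 0.10 per day; in-hospital death proportion p = 0.20; a proportion q = 0.05 of discharged patients die within 28 days of discharge, none of them seen.

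- Death rate in hospital: 0.20 × 0.10 = 0.02 per day. Discharge rate: 0.80 × 0.10 = 0.08 per day.
- In-hospital death by day 28: 0.20 × (1 − e^(−2.8)) = 0.188.
- Post-discharge hazard: μ = −ln(0.95)/28 = 0.00183 per day.
- Post-discharge death by day 28: ∫₀²⁸ 0.08 e^(−0.10u) [1 − e^(−μ(28−u))] du = 0.027.
- True survival: 1 − 0.188 − 0.027 = **78.5%**.
- (a) Discharged patients carried as alive: 1 − 0.188 = **81.2%**, a bias of **+2.7 points**.
- (b) Kaplan-Meier censored at discharge: e^(−0.02 × 28) = e^(−0.56) = **57.1%**, a bias of **−21.4 points**.

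A simulation of 400,000 patients gave 78.5%, 81.3% and 57.3%. The two readings of one dataset differ by 81.2 − 57.1 = 24.1 points.

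**2. Range**

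| In-hospital death | Post-discharge death | True | (a) bias | (b) bias |
|---|---|---|---|---|
| 5% | 0% | 95.3% | 0.0 | −8.4 |
| 5% | 20% | 82.4% | +12.9 | +4.6 |
| 20% | 0% | 81.2% | 0.0 | −24.1 |
| 20% | 5% | 78.5% | +2.7 | −21.4 |
| 20% | 20% | 70.3% | +10.9 | −13.2 |
| 30% | 0% | 71.8% | 0.0 | −28.7 |
| 30% | 20% | 62.3% | +9.5 | −19.1 |

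Over the full grid (in-hospital death 5%, 10%, 20%, 30%; post-discharge death 0%, 2%, 5%, 10%, 20%), (a) runs from 0 to +12.9 points and (b) from −28.7 to +4.6. In 19 of the 20 cells (b) is negative. The rows with no post-discharge death show that (b) is wrong even when no death is missed, because the censoring is informative.

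**3. Partial capture**

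If the network charts half of the post-discharge deaths, bias (a) in the base case falls from 2.7 to 0.5 × 2.67 = 1.3 points.

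**4. What the data alone determine**

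By day 28 in the base case, 0.80 × (1 − e^(−2.8)) = 75.1% have been discharged alive. If none had documented status at day 28, survival could lie anywhere from 81.2 − 75.1 = 6.1% to 81.2%. The 18.8% in-hospital death by day 28 is fully determined.

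**5. Contrast between groups**

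Suppose observed mortality is 30% in nursing-home patients and 15% in others, an observed relative risk of 2.0. Let x and y be the proportions of discharged patients who die unseen. The true relative risk is (0.30 + 0.70x)/(0.15 + 0.85y).

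- x = 15%, y = 2%: 0.405/0.167 = 2.43, so 2.0 understates it.
- x = y = 10%: 0.370/0.235 = 1.57, so 2.0 overstates it.
- The observed value understates the truth only if 0.70x > 1.70y, that is x > 2.43y.

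**The case against.** Several stronger readings are tempting, and the documents do not support them.

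- **That survival is overstated.** This holds only if discharged patients without a charted death are carried as alive. Item 5.71 names Kaplan-Meier with censoring, and censoring at discharge usually errs the other way. The direction cannot be read from the protocol.
- **That the health record is the only source and outside deaths are never seen.** The source list is open. Section 5.5 has structured and unstructured records reviewed, and 6.1 describes a network of several hospitals and clinics. Deaths at readmission or noted later in the chart can be captured. What stands is that capture is incomplete and depends on who returns to the network.
- **That discharge destination is not collected.** The lists are declared partial, and 5.1 says the fields have already been designed. Its absence from a partial list proves nothing, so it needs confirming.
- **That the protocol counts discharge, even to hospice, as a good outcome.** Item 4.15 lists discharge and survival as outcomes and ranks neither.
- **That comorbidity or nursing-home effects are understated.** Step 5 of the working shows the opposite is possible.

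It is also fair to say that this is a descriptive registry and that the Quality Control section warns of the limits of observational data. That warning is general. It does not mention vital status after discharge, and the same section rules out formal secondary review for accuracy.

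Finally, an in-hospital endpoint still misses deaths after discharge. That is true. It narrows the claim to what the source can observe; it does not recover what the source lacks.

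**Conclusion.** The concern holds in this form: survival is promised without a horizon, a data cut, a vital-status source or a censoring rule, from sources that see deaths outside the network incompletely and selectively. The estimate is then biased upward or, usually, downward according to a choice that the plan leaves open.

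In the base case the bias is +2.7 or −21.4 points. These sizes rest on assumed death rates, an assumed 10-day mean stay that was not varied, constant hazards, and no capture of post-discharge deaths unless stated. They show the scale and the ambiguity of sign; they do not predict this registry's error. That missed deaths concentrate in frail patients is plausible but not in the documents, so the effect on subgroup contrasts has no fixed direction.

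The change should be made. A better survival estimator alone would not supply the missing deaths, and a fuller caveat alone would leave 4.15 promising something the named sources cannot reliably deliver.

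**What to change.** In 4.15, 5.64 and 5.71:

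1. Define the index date. For hospitalised patients, make the mortality outcome in-hospital death by a fixed day from it (for example day 30), among patients whose index date is at least that long before a stated data cut.
2. Estimate it by cumulative incidence with discharge alive as a competing event, not by Kaplan-Meier censored at discharge.
3. Confirm or add discharge destination, including hospice. Report hospice discharges separately, and count them with deaths in a sensitivity analysis.
4. Report survival after discharge, and survival in patients never hospitalised, only as 'deaths known to the network'. Give the proportion whose status at the horizon is documented, by discharge destination, with best-case and worst-case bounds for unknown status.

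**Cost.** No patient contact or outside linkage is needed. Recent admissions wait out the horizon before analysis. Some charts already entered may need one more field, possibly filled from a Business Intelligence report. The claim narrows from survival to in-hospital death.

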5.1 Registry Design and Collection

The Hackensack Meridian Health RWD Observational COVID-19, a descriptive observational database, is a multi-center initiative collecting data throughout the Hackensack Meridian Health Network (HMH).

The database will be drawn from the electronic health records of patients with confirmed or suspected COVID-19. HMH utilizes the EPIC system at most of the facilities, which will serve as the primary data source. Additional data obtained via other HMH staff and

bioinformatics can be added to the database as available and permitted. This includes but is not limited to data obtained either directly from EPIC or provided by other sources such as the HMH Business Intelligence Office (BI) to facilitate data extraction. Reports provided by BI can be entered directly into the REDCap database or kept separately (as pre-data supplements that might be added at a later time).

The database will be designed within the REDCap system. REDCap is a secure web application for building and managing online surveys and databases. While REDCap can be used to collect virtually any type of data (including 21 CFR Part 11, FISMA, and HIPAA-compliant environments), it is specifically geared to support online or offline data capture for research studies and operations.

The REDCap hosted universal observational database can export HIPAA compliant files for external analysis as part of the secondary research usage clause defined by the OHRP.

Data collection fields enumerating the common prognostic variables, treatment regimens and clinical outcomes have been designed by the principal investigator and the study team with input from the Centers of Disease Control and Prevention (CDC).

The abstraction process into the database will be performed by members of HMH who are approved to have access to the EPIC system or provided by BI. Outside abstraction, which would involve viewing of PHI, will not be permitted unless specifically granted by the IRB.

